3.5 Risk/Benefit Assessment

Please see the vadadustat Investigator's Brochure for additional discussion and information for the following section.

3.5.1 Known Potential Risks

Trials of injectable ESAs in patients with anemia secondary to NDD-CKD or DD-CKD have demonstrated an increased risk of CV events associated with higher Hb targets (Besarab 1998; Pfeffer 2009a; Singh 2006). Post-hoc analyses performed by the Food and Drug Administration (FDA) and others have shown an association between these adverse outcomes and supraphysiologic serum EPO levels and/or Hb oscillations and overshoots (McCullough 2013; Unger 2010).

In vadadustat nonclinical safety studies, the main findings originated from an exaggerated pharmacological response that results in increased erythropoiesis, polycythemia, blood hyperviscosity, and the formation of fibrin thrombi in multiple organs. Early mortality noted in the mouse and rat and moribundity in the dog were due to the sequelae associated with polycythemia. These findings were reproducible across species and studies, dose-dependent and showed reversibility. Dose-limiting toxicity in the exploratory toxicology studies was due to hemoglobinuric nephropathy (rat) and emesis associated with body weight loss (dog).

In completed Phase 1 clinical studies of vadadustat in healthy subjects, there were low numbers of treatment-emergent AEs. The most frequently reported AEs were in the gastrointestinal disorders (i.e., nausea, diarrhea, abdominal pain, flatulence, dyspepsia) and nervous system disorders (i.e., headache, dizziness) SOC. The majority of AEs were mild to moderate in severity.

The most frequently reported AEs in completed Phase 2 studies of NDD- and DD-CKD subjects were in the following SOCs: gastrointestinal disorders (nausea, diarrhea, vomiting), CV disorders (hypertension, hypotension, coronary artery disease), renal disorders (renal failure chronic, renal failure acute), infections and infestations (gastroenteritis, urinary tract infection, pneumonia), and metabolism and nutrition disorders (hyperkalemia, fluid overload). Four deaths occurred in the completed Phase 2 clinical studies.

An important identified risk of hepatotoxicity associated with vadadustat therapy has been confirmed. There have been reports of drug-induced liver injury (DILI) possibly or probably related to vadadustat including one case of Hy's Law probably related to vadadustat. All subjects recovered without sequelae.

An important identified risk of drug-drug interactions with some statins has been confirmed based on the results of clinical studies and have resulted in the following dose restrictions in subjects taking vadarustat and concomitant statins: the maximum recommended daily dose of rosuvastatin is 10 mg, and the maximum recommended daily dose of simvastatin is 20 mg. Review of the Phase 3 safety data did not identify any safety signal for myopathy and/or rhabdomyolysis.

Other non-important identified risks include abdominal pain, headache, and increased blood uric acid.

3.5.2 Known Potential Benefits

In studies to date, once-daily oral doses of vadarustat increased mean Hb with fewer excursions above the target range of 10.0 to 11.0 g/dL when compared with darbepoetin alfa. In addition, serum EPO levels remained well below those reported with ESAs in the literature. As a result, there is the potential for the investigational drug vadarustat to provide an effective and safe therapeutic option for the treatment of renal anemia.

In addition, vadarustat may enhance iron absorption, transport, and utilization. Phase 1 and Phase 2 studies have demonstrated a consistent dose-dependent increase in TIBC and decrease in ferritin and hepcidin. Mechanistic studies have demonstrated that HIF stabilization downregulates the iron absorption inhibitor hepcidin, and upregulates the iron-mobilizing regulators ferroportin and transferrin (and its receptor) ([Peyssonnaux 2007](#)). Potential clinical benefits include enhanced erythropoiesis and decreased exogenous iron requirements.

3.5.3 Overall Benefit: Risk Conclusion

DD-CKD and associated anemia are serious chronic conditions with significant morbidity and mortality due to the underlying disease as well as associated conditions (including diabetes and cardiovascular diseases including hypertension). Subjects enrolled in this study will be receiving chronic, outpatient in-center hemodialysis TIW, requiring maintenance ESA treatment.

The currently known risks of vadarustat most relevant to the study population are those associated with long-term vadarustat treatment in DD-CKD patients as measured in Study CI-6548-0017. In this study, the overall safety profile was similar to that of darbepoetin alpha. The overall incidence of TEAEs was similar between the vadarustat treatment group (88.3%) and darbepoetin comparator group (89.3%). The most common TEAEs (> 10%) in the vadarustat treatment group were diarrhoea, pneumonia and hypertension.

Drug-related TEAEs were more frequently reported in the vadarustat treatment group (9.6%) than in the darbepoetin alfa treatment group (3.8%). With the exception of Gastrointestinal disorders SOC (with the most common TEAEs being diarrhea [2.2%] and nausea [1.5%]), the incidence of drug related TEAEs was similar between subjects treated with vadarustat (4.2% and darbepoetin alfa (3.7%).

Adverse events of special interest (AESI, see [Section 9.11.8](#)) for vadarustat are malignancy including renal cell carcinoma (also see [Section 9.11.1.2](#)), elevation in ALT or AST >3 times ULN (also see [Section 9.11.1.1](#)), hepatotoxicity, worsening of hypertension, pulmonary hypertension, thrombotic events, congestive heart failure and adrenal disorders.

This study will evaluate efficacy and safety of different vadadustat dosing strategies in hemodialysis subjects converting from ESAs to further characterize the optimal vadadustat regimen, with an emphasis on TIW dosing in hemodialysis patients. This will be the first study in which DD-CKD subjects will receive vadadustat as TIW treatment from the onset of treatment, will receive TIW doses for more than 20 weeks or receive doses > 900 mg of vadadustat. In addition, this will be first study in which vadadustat will be studied against Mircera.

In studies to date, QD oral doses of vadadustat increased mean Hb with fewer excursions above the target range of 10.0 to 11.0 g/dL when compared with darbepoetin alfa. The results of the global Phase 3 clinical development program have confirmed that vadadustat in oral daily doses between 150 – 600 mg is non-inferior to darbepoetin alpha with respect to achieving and maintaining target Hb concentrations. Potential clinical benefits include enhanced erythropoiesis and decreased exogenous iron requirements.

Based on the totality of available information for vadadustat in the proposed patient population, the benefits outweigh the risks for the proposed study.

4.0 OBJECTIVES AND ENDPOINTS

4.1 Primary Objective

To demonstrate the efficacy and safety of vadadustat administered TIW compared to long acting ESA (Mircera) for the maintenance treatment of anemia in hemodialysis subjects.

4.2 Primary Efficacy Endpoint

Mean change in Hb between Baseline (average pretreatment Hb) and the primary evaluation period (average Hb from Weeks 20 to 26, inclusive).

4.3 Secondary Efficacy Endpoint

Mean change in Hb between Baseline (average pretreatment Hb) and the secondary evaluation period (average Hb from Weeks 46 to 52, inclusive).

4.4 Other Endpoints

Other endpoints include the following:

- Proportion of subjects having a Hb value within the target range (10.0 to 11.0 g/dL) during the primary evaluation period (Weeks 20 to 26).
- Proportion of subjects having a Hb value within the target range (10.0 to 11.0 g/dL) during the secondary evaluation period (Weeks 46 to 52).

4.5 Safety Endpoints

4.6 Primary Safety Endpoint

Treatment-emergent AEs and treatment-emergent SAEs.

4.7 Secondary Safety Endpoints

Secondary endpoints include the following:

- Proportion of subjects receiving RBC transfusions from Baseline to Week 26.
- Proportion of subjects receiving RBC transfusions from after Week 26 to Week 52.
- Proportion of subjects with Hb >11.0, Hb >12.0, >13.0, or >14.0 g/dL.
- Proportion of subjects with Hb <7.0, <8.0, <9.0, or <10.0 g/dL.
- Proportion of subjects with Hb increase >1.0 g/dL within any 2-week interval or >2.0 g/dL within any 4-week interval.

4.8 Pharmacokinetic/Pharmacodynamic Endpoints

The PK parameters include the following:

- C_{max}
- C_{tau}

The PD endpoints include the following:

- Erythropoietin (EPO)
- Reticulocyte count
- Markers of iron metabolism (including iron, ferritin, TIBC)

[REDACTED]
[REDACTED]

5.0 STUDY DESIGN

5.1 Overall Design

This is a multi-center, randomized, open-label, active-controlled study of the efficacy and safety of conversion from long-acting ESA (Mircera) to vadadustat TIW for the maintenance treatment of anemia in hemodialysis patients. Following a Screening period of up to 8 weeks (56 days), subjects who meet all inclusion and none of the exclusion criteria will be randomized 1:1:1 to vadadustat 600 mg TIW, vadadustat 900 mg TIW, or to remain on Mircera according to the dialysis center's protocol.

Randomization will be stratified by dialysis organization:

Following randomization, there will be 2 periods during the study:

- **Conversion and Maintenance Period (Weeks 0 to 52):** conversion to vadadustat TIW or to remain on Mircera (Weeks 0 to 20). There will be a primary efficacy evaluation period (Weeks 20 to 26) and a secondary efficacy evaluation period (Weeks 46 to 52).
- **Safety Follow-up Period (Early Termination [ET] and Follow-Up):** post-treatment safety follow up visit (ET/End of Treatment [EOT] +4 weeks) either in person or via telephone.

5.2 Scientific Rationale for Study Design

This study will evaluate the efficacy and safety of dose conversion from a long-acting ESA (Mircera) to TIW vadadustat for the maintenance of treatment of anemia in hemodialysis patients. Numerous studies have demonstrated that hemodialysis subjects requiring higher ESA

doses to treat their anemia have a higher burden of comorbidities, a more inflammatory state, and a greater risk of adverse outcomes (Besarab 1998; Parfrey 2005; Unger 2010). As described above (Section 3.4) in a Phase 2 hemodialysis study (CI-0011), a post-hoc analysis suggested higher pre-baseline ESA doses were associated with lower observed mean Hb levels. Subjects on higher pre-baseline ESA doses may benefit from a higher starting dose of vadadustat after initial conversion from ESAs.

In this study, Mircera was chosen as an active comparator as it is a long-acting Continuous EPO Receptor Activator (CERA) and therefore can be administered less frequently than short- and middle-acting ESAs, while maintaining equivalent efficacy for the treatment of anemia in patients with CKD (Biggar, 2017; Davey, 2018; Mircera USPI 2018; Palmer, 2014). Patients receiving CERA required less frequent ESA administration, demonstrated smaller decreases in Hb levels, and were less likely to require an ESA dose during hospitalization. Overall, CERA showed comparable clinical performance to shorter-acting ESAs while reducing dose frequency in CKD patients receiving hemodialysis (Davey et al, 2018).

This is particularly relevant in the current medical and regulatory climate given the accumulating study findings that resulted in the FDA revising the prescribing information for the currently marketed ESAs. These study results indicate an increased risk of death and adverse CV events, such as stroke and HF, particularly when using ESAs to achieve a higher Hb concentration. In the US, the mortality and CV risks associated with ESAs are outlined in a black-box warning in the prescribing information of ESAs, with a recommendation to use the lowest dose possible to avoid transfusions. While no similar major warnings exist in the European Union (EU) Summary of Product Characteristics (SmPC), there is caution suggested with use of ESAs, and recommendation to keep Hb levels below 12.0 g/dL. Clinical practice guidelines (Locatelli 2013) recommend that risk factors for stroke and malignancy should also be taken into account when making treatment decisions to use ESAs for the treatment of anemia.

5.3 Justification for Dose

In this trial, 2 different vadadustat starting doses will be explored. The starting doses of vadadustat will be 600 mg TIW and 900 mg TIW in subjects converting from Mircera. The dose range for titration is 300 to 1200 mg TIW. Vadadustat 750 and 900 mg QD as titration doses are being studied in an ongoing Phase 2b trial in DD-CKD subjects and as fixed doses in an ongoing Phase 1b trial, DD-CKD subjects. In prior studies, there was minimal accumulation of vadadustat with repeated dosing of up to 900 mg. Given that the half-life of vadadustat in dialysis patients is approximately 8 to 10 hours and the interval between doses will be a minimum of 48 hours (approximately 5 times the half-life), it is expected that during TIW dosing, vadadustat will be eliminated from the systemic circulation without accumulation before the subsequent dose. Therefore, the exposures with 1200 mg single dose is likely to be similar to 1200 mg TIW. Further, per total weekly dosing, 1200 mg TIW (3600 mg/week) is a lower dosing regimen compared to 900 mg QD (6300 mg/week). The starting doses and the proposed vadadustat Dosing and Dose Algorithm (Appendix 1) in this study are designed to maintain Hb in a predictable and controlled manner while minimizing abrupt increases or excessive rises in Hb levels. Based on plasma concentrations and PD measures from previously conducted clinical studies with vadadustat, a population PK/PD model was developed. Using this model and the proposed dosing algorithm, simulations were carried out to evaluate the effects of different starting doses and the resulting Hb responses to support the dosing rationale. Results of the

simulations indicated that the starting doses of 300 and 450 mg QD along with the proposed dosing algorithm are optimal to maintain Hb levels of 10.0 to 11.0 g/dL in the US and 10.0 to 12.0 g/dL outside of the US while minimizing excessive rises. The daily dose of 300 mg equates to a weekly dose of 2,100 mg. That weekly dose would equate to 700 mg TIW. The daily dose of 450 mg equates to a weekly dose of 3,150 mg. That weekly dose would equate to 1050 mg TIW. For dosing simplicity, a single dose strength of 300 mg is being used in this study. Therefore, 600 mg TIW (maximum weekly dosing of 1800) and 900 mg TIW (maximum weekly dosing of 2700 mg) were selected as starting doses for this study.

Hb monitoring, a dose adjustment algorithm ([Section 7.1.2](#) and [Appendix 1](#)), and phlebotomy will be implemented to mitigate the potential risk of a rapid Hb rise, as follows:

- Hb measurements are scheduled at least every 2 weeks to Week 8 and thereafter every 4 weeks.
- The dose adjustment algorithm will target a narrow Hb range, 10.0 to 11.0 g/dL.
- The protocol specifies that phlebotomy may be considered in the setting of high Hb levels (>14.0 g/dL) or a high Hb rate of rise, based on the investigator's judgment.

5.4 End of Study Definition

Study Completion

The study will be considered completed after all randomized subjects have completed their final study visit (Week 52/or ET and Safety Follow-Up at Week 56).

Subject Completion

A subject will be considered as having completed the study after completion of their final study visit (Week 52, Safety Follow-Up at Week 56).

5.5 Number of Study Sites

Approximately 50 investigative sites in the US at outpatient hemodialysis center.

5.6 Subject Input on Study Design

No subject input was obtained on the study design.

6.0 STUDY POPULATION

6.1 Inclusion Criteria

Subjects must meet the following inclusion criteria:

1. ≥ 18 years of age.
2. Receiving chronic, outpatient in-center hemodialysis TIW for end-stage kidney disease for at least 12 weeks prior to SV1.
3. Currently maintained on Mircera (≤ 250 $\mu\text{g}/\text{month}$) with at least 2 doses received within 8 weeks prior to SV2.
4. Mean screening Hb between 8.5 and 11.0 g/dL (inclusive), as determined by the average of 2 Hb values measured by the central laboratory at least 4 days apart between SV1 and SV2.
5. Serum ferritin ≥ 100 ng/mL and transferrin saturation (TSAT) $\geq 20\%$ during Screening.
6. Folate and vitamin B₁₂ measurements \geq lower limit of normal during Screening.

6.2 Exclusion Criteria

Subjects must not meet any of the following exclusion criteria:

1. Anemia due to a cause other than CKD (e.g., sickle cell disease, myelodysplastic syndromes, bone marrow fibrosis, hematologic malignancy, myeloma, hemolytic anemia, thalassemia, or pure red cell aplasia).
2. Clinically meaningful bleeding event in opinion of investigator within 8 weeks prior to Baseline.
3. RBC transfusion within 8 weeks prior to Baseline.
4. Having received any doses of darbepoetin alfa (Aranesp[®]) within 4 weeks prior to Baseline.
5. Having received any doses of epoetin alfa (Epogen[®]) within 1 week prior to Baseline.
6. Anticipated to discontinue hemodialysis during the study.
7. Judged by the Investigator that the subject is likely to need rescue therapy (ESA administration or RBC transfusion) immediately after enrollment in the study.
8. History of chronic liver disease (e.g., chronic infectious hepatitis, chronic autoimmune liver disease, cirrhosis or fibrosis of the liver).
9. Aspartate aminotransferase (AST)/serum glutamic oxaloacetic transaminase (SGOT), alanine aminotransferase (ALT)/serum glutamic pyruvic transaminase (SGPT), or total bilirubin >2 x upper limit of normal (ULN) during Screening. Subjects with a history of Gilbert's syndrome are not excluded.
10. Current uncontrolled hypertension as determined by the Investigator that would contraindicate the use of an ESA.
11. Acute coronary syndrome (hospitalization for unstable angina or myocardial infarction), surgical or percutaneous intervention for coronary, cerebrovascular or peripheral artery disease (aortic or lower extremity), surgical or percutaneous valvular replacement or repair, sustained ventricular tachycardia, hospitalization for HF or New York Heart Association Class IV HF, or stroke within 12 weeks prior to or during Screening.
12. History of new, active or recurrent malignancy within 2 years prior to and during Screening or currently receiving treatment or suppressive therapy for cancer. Subjects with treated basal cell carcinoma of skin, curatively resected squamous cell carcinoma of

skin, or treated cervical carcinoma in situ are not excluded.

13. History of deep vein thrombosis or pulmonary embolism within 12 weeks prior to or during Screening.
14. History of hemosiderosis or hemochromatosis.
15. History of prior organ transplantation (subjects with a history of failed kidney transplant or corneal transplants are not excluded).
16. Scheduled organ transplant from a living donor and subjects on the kidney transplant wait-list who are expected to receive a transplant within 6 months.
17. History of a prior hematopoietic stem cell or bone marrow transplant (stem cell therapy for knee arthritis is not excluded).
18. Known hypersensitivity to vadadustat, Mircera, or any of their excipients.
19. Use of an investigational medication or participation in an investigational study within 30 days or 5 half-lives of the investigational medication (whichever is longer), prior to Screening (subjects may participate in another concurrent study only if that study is a non-interventional, observational investigation).
20. Current exposure to any HIF-PH inhibitor or prior exposure to vadadustat.
21. Subjects with bilateral native nephrectomy.
22. Noncompliance with dialysis session attendance defined as missing more than 1 dialysis session within 8 weeks prior to Baseline.
23. Active Severe Acute Respiratory Syndrome-Related Coronavirus (SARS-CoV-2) during Screening.
24. Females who are pregnant or breastfeeding during Screening or are planning to become pregnant and breastfeeding during the study period, and for 30 days after the final study drug administration.
25. Women of childbearing potential who are unable or unwilling to use 2 acceptable methods of contraception* starting at Screening, throughout the study period and for 45 days after the final study drug administration.
26. Female subjects of childbearing potential who plan to donate ova during the study, and for 30 days after the last dose of study drug.
27. Non-vasectomized male subjects who are unable or unwilling to use an acceptable method of contraception* from time of first dose of study drug until 30 days after the last dose of the study drug.
28. Male subjects who plan to donate sperm during the study and for at least 30 days after the last dose of study drug.
29. Any other reason, which in the opinion of the Investigator, would make the subject not suitable for participation in the study.

**Acceptable forms of contraception include:*

- *Established use of oral, injected or implanted hormonal methods of contraception*
- *Placement of an intrauterine device or intrauterine system*
- *Barrier methods of contraception: condom or occlusive cap (diaphragm or cervical/vault caps) with spermicidal foam/gel/film/cream/suppository.*

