7.1.3 Study Medication Stopping Rules for Liver Function Test Changes

Vadadustat must be permanently discontinued if a subject meets 1 of the following criteria:

- ALT or AST $> 3 \times$ ULN and total bilirubin $> 2 \times$ ULN

- ALT or AST >3x ULN and international normalized ratio (INR) >1.5
- ALT or AST >8x ULN
- ALT or AST remains >5x ULN over 2 weeks (re-challenge generally should be avoided with ALT or AST >5x ULN unless there are no other good therapeutic options)
- ALT or AST >3x ULN with symptoms (e.g., fatigue, nausea, vomiting, right upper quadrant pain, fever, rash) or eosinophilia

See [Section 9.11](#) for reporting requirements related to a subject being permanently discontinued based on meeting the laboratory abnormalities listed above.

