Abnormal Test Findings – All laboratory test results will be reviewed by the Investigator. The Investigator will utilize his/her judgment in determining if out-of-range laboratory values are clinically significant and will denote this using the abbreviation “CS” on the laboratory report for source documentation. Laboratory tests that are labeled as clinically significant should be reported as AEs, either separately or as part of a description of a symptomatic AE. If there are significant changes in a laboratory report from a previous visit that are determined to be clinically significant, these should also be reported as AEs. Any abnormal laboratory value which requires treatment or further diagnostic testing and/or results in discontinuation from study should be reported as an AE. An expected laboratory abnormality from a condition that is part of the medical history is not considered clinically significant for the purposes of the study unless it represents a worsening of the condition.

Abnormalities in ALT, AST, and Total Bilirubin – Abnormalities in ALT, AST, and total bilirubin should be reported to the Sponsor’s Medical Monitor or CRO designee within 24 hours of awareness as an SAE with ‘other medically important event’ criteria selected, if the following conditions are met:

- New elevation in ALT or AST $>3 \times$ ULN

If new elevations in ALT or AST $>3 \times$ ULN, **without** an elevation of total serum bilirubin $>2 \times$ ULN are identified, the following steps are to be taken:

- Temporary discontinuation of study medication;
- Repeat testing of ALT, AST, alkaline phosphatase (ALP), and total bilirubin, to be completed within 48 to 72 hours to confirm the abnormalities and to determine trend;
- Study medication should not be resumed until monitoring indicates abnormalities have resolved or are stable.

Details on the management of subjects with other ALT and AST abnormalities are further described in [Section 7.1.3](#).

Worsening of Anemia – In this study, it is possible that some subjects may experience a worsening of anemia. As the primary endpoint of this study assesses Hb response, worsening of anemia is captured as part of this efficacy parameter. Worsening of anemia should not be considered an AE unless the worsening of anemia is associated with a cause *other than* the subject’s CKD.

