3.4 STUDY MEDICATION STOPPING RULES

Vadadustat must be permanently discontinued if a subject meets 1 of the following criteria:

- ALT or AST >3x ULN and total bilirubin >2x ULN
- ALT or AST >3x ULN and international normalized ratio (INR) >1.5
- ALT or AST >8x ULN
- ALT or AST remains >5x ULN over 2 weeks (re-challenge generally should be avoided with ALT or AST >5x ULN unless there are no other good therapeutic options)

-
- ALT or AST >3x ULN with symptoms (e.g., fatigue, nausea, vomiting, right upper quadrant pain, fever, rash) or eosinophilia
 - undergo a solid organ (including kidney), hematopoietic stem cell, or bone marrow transplantation

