6.12.2.2 Liver Function Abnormality

A summary of liver function abnormalities by analysis period will be provided. Any subject with at least 1 of the following liver function abnormalities will be summarized:

- Alanine aminotransferase (ALT) >2x and <=3x upper limit of normal (ULN)
- ALT >3x and <=5x ULN;
- ALT >5x and <=10x ULN;
- ALT >10x ULN
- Aspartate aminotransferase (AST) >2x and <=3x ULN;
- AST >3x and <=5x ULN;
- AST >5x and <=10x ULN;
- AST >10x ULN
- Total bilirubin >2x and <=3x ULN;
- Total bilirubin >3x ULN

In addition, a table will summarize the occurrence of events that satisfy the following criteria of liver injury:

- (ALT or AST >3x ULN and <=5x ULN) and total bilirubin >2x ULN;
- (ALT or AST >5x ULN and <=10x ULN) and total bilirubin >2x ULN;
- ALT or AST >10x ULN and total bilirubin >2x ULN

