6.12.2.3 Other Laboratory Safety Endpoints

Descriptive statistics for laboratory values (in US conventional and SI units) and changes from baseline at each analysis visit will be summarized for the following laboratory parameters collected in the study including but not limited to the following:

- Complete blood count (CBC): Hb, hematocrit, red blood cell (RBC), MCV, MCH, MCHC, platelets, RDW, white blood cell (WBC) with differential (neutrophils, lymphocytes, monocytes, eosinophils, basophils), reticulocyte count
- Serum chemistry: sodium, potassium, bicarbonate, chloride, calcium, magnesium, phosphorus, glucose, creatinine, BUN, CPK, uric acid, albumin, total protein
- Liver function tests: Total bilirubin, ALP, ALT/SGPT, AST/SGOT, LDH
- Iron indices: Iron, ferritin, TSAT, TIBC
- Lipid Profile: Total cholesterol, LDL, HDL, Triglycerides
- CRP
- EPO

A summary of the number and percentage of subjects experiencing clinically significant values for the following parameter definitions will be presented by analysis period:

- Potassium >6.0 mmol/L

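### Exclusion 9 sets no bilirubin ceiling for Gilbert's syndrome, while the SAP liver tables and the stopping rule use a fixed bilirubin >2x ULN with no Baseline reference

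*Protocol*

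**What the plan says.** **Entry.** Protocol 6.2, exclusion 9 (repeated in the synopsis) bars AST, ALT or "total bilirubin >2 x upper limit of normal (ULN) during Screening. Subjects with a history of Gilbert's syndrome are not excluded". No separate bilirubin limit is given for subjects with Gilbert's syndrome, and the sentence does not say which of the three tests it waives.

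**Stopping.** Protocol 7.1.3 opens with "Vadadustat must be permanently discontinued if a subject meets 1 of the following criteria". The one criterion that involves bilirubin, repeated in SAP 3.4, is "ALT or AST >3x ULN and total bilirubin >2x ULN". It has no Baseline term and no provision for Gilbert's syndrome.

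**Temporary hold.** For a new ALT or AST above 3x ULN without bilirubin above 2x ULN, protocol 9.11.1.1 calls for "Temporary discontinuation of study medication" and repeat testing. The word new applies to ALT and AST, not to bilirubin.

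**Tables.** SAP 6.12.2.2 plans two outputs.
- The first is introduced by "A summary of liver function abnormalities by analysis period will be provided" and has two rows on bilirubin alone, the lower being "Total bilirubin >2x and <=3x ULN".
- The second lists criteria of liver injury. Its three rows all combine ALT or AST with bilirubin, the first being "ALT or AST >3x ULN and <=5x ULN) and total bilirubin >2x ULN".

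No row in either output refers to Baseline.

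**The concern.** If the exemption waives the bilirubin limit, a subject can have a bilirubin above 2x ULN before the first dose. A fixed cut-off then cannot separate a value the subject brought into the trial from one that arose on treatment. In the two-part criterion, the bilirubin half is already met on Day 1, so an ALT or AST rise alone decides the classification.

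This matters because protocol 3.5.1 names hepatotoxicity as a confirmed risk of vadadustat and reports one Hy's Law case. Combined rows usually hold few subjects, so one subject placed there by a long-standing bilirubin value would be noticed. There is also a conduct side. The stopping rule is written for vadadustat only, and under protocol 8.1.2 a subject who permanently stops study medication leaves the study.

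**Working it through.** The plan gives no figure on this point to reproduce. The check has two parts: apply the written rules to example values, then see how large the effect could be.

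**Part 1: the rules applied.** Let *a* be ALT or AST and *b* total bilirubin, both in multiples of ULN.
- Permanent stop, bilirubin criterion (protocol 7.1.3, SAP 3.4): *a* > 3 and *b* > 2.
- Temporary hold (protocol 9.11.1.1): new *a* > 3 and not *b* > 2.
- Bilirubin-only rows (SAP 6.12.2.2): 2 < *b* ≤ 3, or *b* > 3.
- Combined rows (SAP 6.12.2.2): *b* > 2 with *a* in 3 to 5, 5 to 10, or above 10.

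The comparison is between *b* = 0.8 and *b* = 2.5, where 2.5 is present at entry and unchanged on study. Assume a vadadustat subject with a single raised value and no INR, symptom or eosinophilia criterion met. The ALT-only and AST-only rows are the same in both columns and are left out.

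| *a* | *b* = 0.8 | *b* = 2.5, unchanged since entry |
|---|---|---|
| 1, 2, 2.9 | no bilirubin row, no hold, no stop | bilirubin-only row; no combined row; no stop |
| 3.1, 4 | temporary hold; no combined row | bilirubin-only row; combined row (3 to 5); permanent stop |
| 6 | temporary hold; no combined row | bilirubin-only row; combined row (5 to 10); permanent stop |

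Above 8x ULN, or above 5x ULN for more than 2 weeks, protocol 7.1.3 requires a stop whatever the bilirubin. The difference in stopping is therefore confined to rises above 3x ULN that meet no other criterion.

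**Part 2: possible size.** The planned vadadustat total is 2 × 150 = 300. The documents give neither the frequency of Gilbert's syndrome nor the share of such subjects above 2x ULN. Both are assumed here: 2% to 8%, and 10% to 50%.
- Low: 300 × 0.02 × 0.10 = 0.6 subjects (0.2%).
- High: 300 × 0.08 × 0.50 = 12 subjects (4.0%).

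These are counts in the bilirubin-only rows. For the combined rows, assume further that 1% to 3% of these subjects have ALT or AST above 3x ULN on study.
- Low: 0.6 × 0.01 = 0.006.
- High: 12 × 0.03 = 0.36.

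So fewer than one combined count would be expected on vadadustat. The same shares in the 150 Mircera subjects give 0.3 to 6 in the bilirubin-only rows, so the expected proportion is equal in all arms.

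**Comparison within the SAP.** Section 6.12.4 includes blood-pressure rows that pair a threshold with a rise of at least 20 mmHg from Baseline. Section 6.12.1 counts an adverse event as treatment-emergent only if it starts or worsens after treatment begins. The liver rows use neither idea.

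**The case against.** The case on the other side is substantial.

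- **The injury rows and the bilirubin stopping criterion both need ALT or AST above 3x ULN.** This stands. Because exclusion 9 bars ALT or AST above 2x ULN, such a value would normally be a new rise, and protocol 9.11.1.1 already makes it a reportable serious event. A reader might infer that pre-existing bilirubin is by itself scored as on-study liver injury. The text does not support that.
- **No liver conclusion turns on one count.** This also stands. SAP 6.12.2.2 plans summaries only, with no test or threshold. A reader might infer that one or two misplaced subjects could reverse the liver conclusion; nothing in the plan or in the figures above shows that.
- **Safeguards exist.** Protocol 11.11 has a hepatic panel adjudicate possible liver effects. SAP 6.12.2.3 plans that "Descriptive statistics for laboratory values (in US conventional and SI units) and changes from baseline at each analysis visit will be summarized", and total bilirubin is on its list. SAP Table 1 includes Baseline as an analysis period, so the abnormality table may show Baseline counts. Medical history is coded. These limit the harm, but group means and marginal counts do not show which on-study subjects were already above 2x ULN, and the legible SAP text does not tie the rows to adjudication.
- **Randomization balances these subjects in expectation.** True for the bilirubin-only rows, which are inflated rather than biased between arms. It does not alter a stopping rule written for vadadustat only.
- **The exemption may mean only that the diagnosis does not exclude.** Possible. But the sentence sits inside the laboratory criterion, so waiving the bilirubin limit is its natural function. Extending it to AST and ALT is the least natural reading; the wording simply does not rule it out.
- **Protocol 7.1.3 and 9.11.1.1 do not conflict.** Correct. One covers bilirubin above 2x ULN, the other its absence. The unresolved point is how both relate to the entry exemption.

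**Conclusion.** The point holds in a limited form. On the natural reading of exclusion 9, a subject with Gilbert's syndrome and a stable bilirubin above 2x ULN is counted in the SAP bilirubin-only abnormality rows with no on-study change. A later ALT or AST above 3x ULN then leads to a combined row and, on vadadustat, to the permanent-stop criterion instead of the temporary hold, although bilirubin has not moved.

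The number affected is unknown and probably small. The range of 0.6 to 12 of 300 applies only to the bilirubin-only rows, and both its inputs are assumptions; the 20-fold spread shows how little they settle. The combined-row figure of 0.006 to 0.36 adds a third assumption. No efficacy hypothesis is touched directly. This is a minor reporting improvement, worth making because it is cheap and follows the SAP's own practice elsewhere.

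**What to change.** **SAP 6.12.2.2.** Keep the fixed-threshold rows. Add a shift-from-Baseline summary of total bilirubin category, using the SAP 6.1 definition of Baseline. In the bilirubin-only and combined rows, show subjects with Baseline bilirubin above 2x ULN on a separate line. The Schedule of Activities already has liver function tests at Screening and Baseline, so no new data are needed. The cost is programming, one small shift table and an extra table line.

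**Protocol 6.2, exclusion 9, and the synopsis.** State which of AST, ALT and total bilirubin the Gilbert's exemption covers. The cost is a clarifying phrase.

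**Reconciliation.** The sponsor should reconcile exclusion 9 with the bilirubin condition in protocol 7.1.3, protocol 9.11.1.1 and SAP 3.4 for subjects who enter above 2x ULN. Which rule should apply to them is a clinical decision, and none is proposed here.
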